13.2.2.8 Assessment of Pain Using the NRS

The average daily assessment will be calculated separately for dysmenorrhea and pelvic pain within each key 28-day baseline and treatment period. The percentage change from baseline NRS pain score will be analyzed within treatment group and between treatment groups. An overall comparison among the 3 treatment groups will be performed using a one-way Analysis of Variance. Pairwise comparisons of the treatment groups will be made using t-test or non-parametric test as appropriate. While the primary assessment will be based on scores during the 28-day period prior to Visit 12 (after 18 weeks of treatment), summaries will also be prepared for each of the other visits.

The average daily assessment of dysmenorrhea and pelvic pain scores collected during the active treatment stage of the study (Stage 3) will also be summarized.

13.3 General Statistical Issues

A Statistical Analysis Plan (SAP) will be developed prior to the analyses of the first cycle of treatment. Two analyses will be conducted. The first analysis will occur when all subjects have completed the first cycle of treatment (Week 18) and the second will be conducted once all subjects have completed the active treatment stage of the study (Stage 3).

Statistical significance will be declared if the two-sided p-value is ≤ 0.05 . Since the study was not powered for efficacy assessments based on statistical hypotheses, the p-values reported at the conclusion of the study are being reported to quantify the difference in the treatment effect between treatment groups.

14. ETHICS

14.1 Subject Information and Consent

A properly executed, written informed consent in compliance with Food and Drug Administration (FDA) regulations and Good Clinical Practice (GCP) guidelines will be obtained from each subject prior to entering the study or performing any unusual or non-routine procedure that involve a risk to the subject. The Principal Investigator will submit a copy of the informed consent document to the Institutional Review Board for review and approval before research subjects are enrolled. The Principal Investigator will provide a copy of the signed informed consent to the subject and the original will be maintained in the subject's medical record.

14.2 Institutional Review Board

The Principal Investigator will provide the Institutional Review Board with all requisite material, including a copy of the informed consent. The study will not be initiated until the IRB provides written approval of the protocol and the informed consent and until approved documents have been obtained by the Principal Investigator and copies received by the Sponsor. Appropriate reports on the progress of this study by the Principal Investigator will be made to the Institutional Review Board and the Sponsor in accordance with the applicable government regulations and in agreement with the policy established by the Sponsor.

14.3 Monitoring Case Report Forms

Repros Therapeutics Inc. or their designee will monitor all aspects of the study with respect to current GCP and standard operating procedures for compliance with applicable federal regulations. These individuals will have access to all records necessary to ensure integrity of the data and will periodically review progress of the study with the Principal Investigator.

14.4 Study Record Retention

In accordance with FDA regulations and GCP guidelines, all study-related documentation shall be retained by the Principal Investigator for a minimum of 2 years after FDA approval of telapristone acetate or clinical development has been terminated. At that time, the Principal Investigator will contact Repros Therapeutics Inc. regarding further disposition of the study records and comply with instructions.

14.5 Data Quality Assurance

All data recorded during the study will be available for audit against source data and for compliance with GCP and specific protocol requirements. Monitoring of the study progress and conduct will be ongoing. The Principal Investigator will be responsible for the following:

1. Monitoring study conduct to ensure that the rights of subjects are protected;
2. Monitoring study conduct to ensure trial compliance with GCP guidelines; and
3. Monitoring accuracy, completion and verification from source documents of study data.

14.6 Confidentiality

All information provided to the Principal Investigator by Repros Therapeutics Inc. or their designees including non-clinical data, protocols, CRFs and verbal and written information will be kept strictly confidential and confined to the clinical personnel involved in conducting the study. It is recognized that this information may be released in confidence to the IRB. In addition, no reports or information about the study or its progress will be provided to anyone not involved in the study other than to Repros Therapeutics Inc. or their designees or in confidence to the IRB, except if required by law.

14.7 Publications

Following completion of the study, the data from the entire study or from subsets of the study may be considered for reporting at a scientific meeting or for publication in a scientific journal, in which case Repros Therapeutics Inc. will be responsible for these activities and will work with the Principal Investigator to determine how the manuscript is written and edited, the number and order of authors, the publication to which it will be submitted and other related issues.

[figure not shown]

VAS	Visual Analog Scale
WBC	White blood cell

1. INTRODUCTION

This statistical analysis plan (SAP) describes the data analysis specifications for stage 2 of study ZPE-202, entitled “A Phase 2, Multi-Center, Three-Arm, Parallel Design, Randomized, Double-Blind Study to Evaluate the Safety and Efficacy of 6 and 12 mg Proellex® (Telapristone Acetate) Administered Orally in the Treatment of Premenopausal Women with Confirmed Endometriosis”. The preparation of this version of the SAP adheres to Amendment 9 of the ZPE-202 protocol.

Two separate analyses are planned. The first analysis will occur once all subjects have completed the placebo-controlled (stage 2) portion of the study, and will only include data from the placebo-controlled (stage 2) and baseline assessment (stage 1) portions of the study. The second analysis will occur once all subjects have completed the active treatment portion of the study (stage 3), and will include all data collected during the study.

This SAP will focus on analyses for stage 2. Another SAP will focus on analyses for stage 3.

2. STUDY OBJECTIVES

The purpose of this study is to determine the safety and efficacy of two doses of Proellex in premenopausal women with pelvic pain associated with endometriosis confirmed within the last seven years and using prescription analgesics for symptomatic pain.

3. STUDY DESIGN

3.1 OVERVIEW AND LENGTH OF STUDY

ZPE-202 is a phase 2, 3-arm study with an 18 week active dosing period and an option to extend treatment for 2 additional cycles. The study will be conducted in three stages.

In the first stage, women will undergo a baseline assessment period with placebo or no study medication until their second ovulation event. Endometriosis pain, dysmenorrhea, non-

[REDACTED]

In the second stage (placebo-controlled), following the baseline assessment period, subjects will be randomized into one of 3 arms (placebo, 6 mg Proellex, 12 mg Proellex) in a 1-1-1 fashion. The start of the 18 week dosing period for the first cycle of treatment should commence as soon after ovulation as possible, after which subjects will be followed until menses returns. Subjects who do not wish to receive additional cycles of treatment after stage 2 will have their last visit scheduled after blood flow has stopped. During this off-drug interval subjects will continue to record study information in the daily diaries.

After completing a minimum of 28 days of treatment in the second stage of the study, subjects may discontinue the study and still be eligible to qualify for 2 additional treatment cycles.

In the third stage (active treatment), subjects who are eligible to receive additional cycles of treatment and who elect to continue treatment will be scheduled to start dosing in their next course 21 days (+/- 2 days) after the start of bleeding, following the first menses after the end of

their first course of treatment (off-drug interval). Subjects will receive 2 courses of additional active treatment separated by an off-drug interval (ODI), after which they will continue to record study information in the daily diary. Subjects randomized to placebo in the second stage will receive 12 mg of Proellex in this stage. Those randomized to Proellex in the second stage will retain their current dose level for the duration of this stage. The final follow-up visit will be scheduled after blood flow has stopped.

3.2 SAMPLE SIZE CALCULATION/JUSTIFICATION

Up to 60 female subjects, 20 per dose arm, meeting the inclusion/exclusion criteria will be randomized in a 1-1-1 fashion. The sample size was powered based on the two-sample t-test that will be used to make pairwise comparisons between treatment groups. It is anticipated that

4. ANALYSIS SETS

4.1 INTENT-TO-TREAT POPULATION

The ITT population will consist of all patients who are randomized and receive study drug.

4.2 SAFETY POPULATION

The Safety population will consist of all patients who are randomized, receive study drug, and have some post-baseline safety data.

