6.3 EXTENT OF EXPOSURE

The duration of exposure will be calculated for each subject. Summary statistics will be presented using the Intent-to-Treat population.

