6.8 SAFETY ANALYSES

The safety analyses will be conducted using the Safety population, as defined in Section 4.2.

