6.8.1 Adverse Events (AEs)

Treatment-emergent AEs (TEAEs) are defined as those AEs with an onset date and time equal to or after the start of study medication in stage 2, or those events in which the onset date and time are before the start of study medication but worsened after the start of study medication. To be conservative, in the case of a missing onset time for an AE, an AE with a start date equal to or after the dosing date will be considered treatment-emergent. AE's with missing onset dates will also be considered treatment-emergent.

All TEAEs will be summarized by treatment group. The number of TEAEs as well as the number and percentage of subjects who experienced at least one TEAE will be summarized for each system organ class and each preferred term. The percentage will be based on the number of subjects included in the Safety population. Each subject will contribute at most one count per summarization category.

If a subject has more than one AE that codes to the same preferred term, the subject will be counted only once for that preferred term. Similarly, if a subject has more than one AE within a system organ class category, the subject will be counted only once for that system organ class category.

TEAEs will also be summarized by maximum severity and by strongest relationship to treatment. Serious adverse events (SAEs) will be tabulated and listed in a manner similar to TEAEs. A listing of all AE data will be provided to supplement the tabulated results.

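### SAP 4.2 admits a treated woman to the Safety population only if she has post-baseline safety data, so adverse-event percentages may not cover all exposed women

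*SAP*

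**What the plan says.** SAP 4.1 defines the ITT set by randomization and treatment alone: "The ITT population will consist of all patients who are randomized and receive study drug". SAP 4.2 adds a data condition: "The Safety population will consist of all patients who are randomized, receive study drug, and have some post-baseline safety data". Neither the kind nor the amount of data that would satisfy it is specified.

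SAP 6.8 applies the narrower set to safety: "The safety analyses will be conducted using the Safety population, as defined in Section 4.2". SAP 6.8.1 makes it the denominator of the TEAE tables: "The percentage will be based on the number of subjects included in the Safety population". Extent of exposure (SAP 6.3) goes the other way: "Summary statistics will be presented using the Intent-to-Treat population". Disposition (6.4) and deviations (6.5) are also on ITT.

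The visible text plans no adverse-event analysis on all treated women and no count of those excluded. The visible protocol sections give no Safety definition of their own.

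**The concern.** Having safety data after baseline is something that happens, or fails to happen, after randomization. A set that depends on it can differ between arms for reasons connected with treatment. A woman who takes study drug and is then lost before giving any safety information is exposed with unknown outcome. Under SAP 4.2 the adverse-event tables leave her out, whereas the exposure table includes her.

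Safety is half of the stated objective (SAP 2; Protocol 7). With 20 women planned per arm, each is 5% of her arm. What is at stake is whether a TEAE percentage can be read as a proportion of the women exposed, and whether the exposure and adverse-event tables describe the same women.

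**Working it through.** **Plan's own figure.** The documents state no number that depends on this definition, so there is nothing to reproduce. The check is set logic followed by simple proportions.

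**Set logic.** ITT requires randomization and receipt of drug. Safety requires both of these plus some post-baseline safety data. Safety is therefore a subset of ITT, and the difference between them is exactly the treated women without such data. If there are none, the two sets coincide.

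**Inputs.**
- n = 20 treated per arm. SAP 3.2: "Up to 60 female subjects, 20 per dose arm, meeting the inclusion/exclusion criteria will be randomized in a 1-1-1 fashion". This takes all 20 as treated.
- x = women in the arm with at least one TEAE. Illustrative values are 4 and 1.
- k = treated women in the arm without post-baseline safety data. The documents do not give k; I assume 0 to 4 to show the range.

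**Direction.** A woman with a recorded TEAE has post-baseline safety data, so x does not change. Only the denominator shrinks, and each percentage is multiplied by n/(n − k) = 20/(20 − k): 1.053, 1.111, 1.176 and 1.250 for k = 1 to 4.

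**Results.** Percentage under the SAP rule, x/(n − k), against all treated, x/n. The last column, (x + k)/n, supposes that every woman with unknown outcome had an event.

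| x | k | x/n | x/(n − k) | (x + k)/n |
|---|---|---|---|---|
| 4 | 0 | 20.0% | 20.0% | 20.0% |
| 4 | 1 | 20.0% | 4/19 = 21.1% | 5/20 = 25.0% |
| 4 | 2 | 20.0% | 4/18 = 22.2% | 6/20 = 30.0% |
| 4 | 3 | 20.0% | 4/17 = 23.5% | 7/20 = 35.0% |
| 4 | 4 | 20.0% | 4/16 = 25.0% | 8/20 = 40.0% |
| 1 | 1 | 5.0% | 1/19 = 5.3% | 2/20 = 10.0% |
| 1 | 2 | 5.0% | 1/18 = 5.6% | 3/20 = 15.0% |

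The SAP percentage lies between the two bounds. It amounts to assuming that the women without data had events at the same rate as the others in their arm.

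**Unequal exclusions.** With 4 of 20 affected in both arms, no exclusions in one arm and 1 or 2 in the other, the gap is 21.1 − 20.0 = 1.1 or 22.2 − 20.0 = 2.2 percentage points, produced by the denominator alone. A gap can also narrow. Take 4/20 on active and 3/20 on placebo, a difference of 5.0 points. If two placebo women are excluded, placebo reads 3/18 = 16.7% and the difference is 3.3 points.

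**The case against.** The strongest objection is that a reader might infer from SAP 4.2 that early losses after dosing are hidden or that events disappear. The documents do not support either inference. Disposition, exposure and deviations are on ITT, so an early loss is still reported; if table Ns are printed, ITT N minus Safety N gives the number excluded. A woman with a recorded event stays in, and SAP 6.8.1 also promises a listing of all adverse-event data. Within an arm the rule can only raise a percentage. All of this stands.

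Exclusions may also be few. The data condition is easy to meet: randomization is at Visit 3 and Week 18 is Visit 12 (Protocol 8.2.3 and 13.2.2.1), with daily diaries throughout. The documents do not say that anyone will lack data, so it would be wrong to state that the denominator is smaller; it may be. The shift is also small against sampling error, since the exact 95% interval for 4/20 runs from about 6% to 44%, and SAP 6.8.1 specifies no between-arm test that it would affect. These points limit the size of the issue but do not make the definition sound.

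Finally, an all-treated denominator has its own bias, because it counts unknown outcomes as event-free. That is correct, and it is why the number of unknowns has to be reported with the percentage.

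One limit on the check itself: only 6.8.1 is visible under SAP 6.8, and the protocol's safety-analysis text is not shown, so a count of missing safety assessments may be planned elsewhere.

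**Conclusion.** The point holds as a conditional and minor one. If at least one randomized, treated woman has no post-baseline safety data, TEAE percentages use a smaller denominator than the exposure table, and the adverse-event tables do not describe all exposed women. Assuming 1 or 2 of 20 excluded in an arm, 4 women with an event read as 21.1% or 22.2% instead of 20.0%, and unequal exclusions can move a between-arm difference by a similar amount in either direction. With no exclusions the effect is nil. These sizes rest on the planned 20 per arm and on an assumed number of exclusions that the documents do not supply. The case for changing the definition is that it turns on an unspecified post-randomization condition and gives two related tables different populations, not that the SAP conceals harm.

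**What to change.** In SAP 4.2, define the Safety population as all randomized women who received at least one dose of stage 2 study drug, and use it for both extent of exposure (6.3) and adverse events (6.8). Both qualifiers are needed. SAP 3.1 allows placebo in stage 1, so a bare one-dose rule could admit women who were never randomized, and SAP 6.8.1 already dates treatment emergence from stage 2 medication.

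In each adverse-event table, show by arm the number k with no post-dose safety data. State that x/n is a lower bound on the proportion of treated women with an event, and that (x + k)/n is the upper bound.

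The cost is a change of wording in SAP 4.2 and 6.3 and one extra line per table; no new data or visits are needed. The downside is that percentages fall slightly where k is above zero (from 21.1% to 20.0% in the one-exclusion example), because women with unknown outcomes are now in the denominator. Without the count beside it, the lower figure could be mistaken for complete ascertainment.

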5. ENDPOINTS

Efficacy endpoints will be:

- Changes in patient and physician reported BBSS scores
- Number of subjects becoming amenorrheic
- Changes in pain assessments
- Changes in analgesic use

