10. ASSESSMENT OF EFFICACY

10.1 Study Endpoints

Primary Endpoint

- Change and percent change in the individual BBSS scores of the three patient reported outcomes (dysmenorrhea, dyspareunia and non-menstrual pelvic pain) by study visit and treatment cycle.

Secondary Endpoints

- Change in daily average use and percent change of prescription medications from the baseline menstrual cycle to the matching period leading up to Week 18, the last day of dosing of the first cycle of treatment.
- Change in daily average use and percent change of over the counter medications from the baseline menstrual cycle to the matching period leading up to Week 18, the last day of dosing of the first cycle of treatment, calculated based on days with reported values.
- Change in daily average use and percent change of overall medication use, prescription and over the counter, from the baseline menstrual cycle to the matching period leading up to Week 18, the last day of dosing of the first cycle of treatment, calculated based on days with reported values.
- Change and percent change in BBSS score incorporating the two physician-reported scores by study visit and treatment cycle.
- Change from baseline in endometrial pain assessed using a Visual Analog Scale (VAS) by study visit and treatment cycle.
- Change from baseline in daily average dysmenorrhea and non-menstrual pelvic pain using an 11-point numerical rating scale (NRS) by study visit and treatment cycle.

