13.2.2.5 BBSS Patient Reported Scores

The percent change from baseline in each of the daily average combined BBSS patient-reported scores (dysmenorrhea, dyspareunia and non-menstrual pelvic pain) will be analyzed to compare the baseline menstrual cycle to a similar period leading up to the last day of dosing in Cycle 1 (Week 18). An overall comparison among the 3 treatment groups will be performed using a one-way Analysis of Covariance, including baseline BBSS score and treatment in the model. Pairwise comparisons of the treatment groups will be made using a two-sample t-test. While the primary assessment will be based on Visit 12 (after 18 weeks of treatment) summaries will also be prepared for each of the other visits. [REDACTED]

The BBSS patient scores during the active treatment stage of the study (stage 3) will also be summarized

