6.7.5 BBSS Patient Reported Scores

Patient reported daily BBSS component scores (dysmenorrhea, pelvic pain, dyspareunia) and total score and the change from baseline in each will be summarized from patient diaries.

The statistical significance of the change from baseline within treatment groups will be based on a paired t-test or Wilcoxon signed-rank test, as appropriate. The change from baseline will be compared between groups using a t-test or Wilcoxon rank-sum test, as appropriate.

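### The visible SAP designates no primary endpoint, visit or dose contrast and departs from the protocol's BBSS analysis, while the protocol's primary is three scores with no success rule

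*SAP*

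**What the plan says.** **Protocol (latest text).** Section 10.1 separates one primary endpoint from the secondary ones. The primary is "Change and percent change in the individual BBSS scores of the three patient reported outcomes (dysmenorrhea, dyspareunia and non-menstrual pelvic pain) by study visit". It is also to be given per cycle of treatment. Physician BBSS, VAS, NRS and medication use are secondary. Section 8.1 lists the same three patient scores twice, once as primary and again as secondary.

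Section 13.2.2.5 gives the analysis. The variable is "The percent change from baseline in each of the daily average combined BBSS patient-reported scores", comparing the baseline cycle with a similar period ending at Week 18. It continues: "An overall comparison among the 3 treatment groups will be performed using a one-way Analysis of Covariance", with baseline BBSS in the model, then pairwise two-sample t-tests. The primary assessment is at Visit 12. Section 13.1 states 80% power with 18 per group on a pairwise t-test, with 20 per arm planned. Section 13.3 sets significance at a two-sided 0.05, and says that the study was not powered for hypothesis-based efficacy assessment and that p-values serve to quantify differences.

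**SAP.** Section 1 says the plan adheres to Amendment 9. Section 5 reads "Efficacy endpoints will be" followed by four topics of equal standing; the first is "Changes in patient and physician reported BBSS scores". Section 6.7.5 covers three components and a total, as change from baseline. For the arms it says: "The change from baseline will be compared between groups using a t-test or Wilcoxon rank-sum test, as appropriate". Section 6.1 lists ANOVA and Kruskal-Wallis among general techniques and sets significance at 0.05. Section 6.2 makes no multiplicity adjustment.

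**The concern.** Protocol 13.2 relies on the SAP to set out all planned analyses in detail before the placebo-controlled data are unblinded. For the primary scores the visible SAP does not do so. An analyst holding both documents still has to decide four things:

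- which of three components, or the total, carries the result;
- whether the metric is change (SAP) or percent change (protocol 13.2.2.5);
- whether the model is a baseline-adjusted ANCOVA (protocol) or an unadjusted t-test or rank-sum test (SAP);
- which dose contrast comes first, or whether either is enough.

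If these are settled after the arms are known, a nominal p ≤ 0.05 on one score at one dose cannot be read as a 5% error. The 80% power figure describes one pairwise test, so it does not describe the chance of success under a rule over three scores.

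**Working it through.** **Side by side, for the patient BBSS scores**

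| Item | Protocol | Visible SAP |
|---|---|---|
| Status | Primary (10.1); also secondary in 8.1 | Not labelled (5) |
| Scores | Three components | Three components and total (6.7.5) |
| Metric | Change and percent change (10.1); percent change (13.2.2.5) | Change (6.7.5) |
| Time | By visit and cycle (10.1); Visit 12 (13.2.2.5) | None named |
| Overall test | Three-group ANCOVA with baseline | None in 6.7.5 |
| Pairwise test | Two-sample t-test, pairs not ordered | t-test or rank-sum, pair not named |
| Success rule | None | None |
| Multiplicity | No procedure visible | No adjustment (6.2) |

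**The plan's power figure.** The assumed effect and SD are not visible, so the calculation can only be run backwards from n = 18, power 0.80 and two-sided alpha 0.05. By the normal approximation d = (1.960 + 0.842) × √(2/18) = 0.934. By the exact noncentral t, d = 0.961. At d = 0.961, 20 per arm gives 84.2% power for one contrast on one score.

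**False-positive chance.** Inputs: three arms of 20, no true effect, one visit, one metric, two-sided t-tests at 0.05. The correlation between scores is an assumption, shown as a range.

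- Six independent tests: 1 − 0.95⁶ = 26.5%. This ignores the shared placebo arm and any correlation between scores.
- Simulated, three scores × two doses versus placebo: 24.9%, 23.6%, 22.1%, 19.1% and 15.0% at correlation 0, 0.3, 0.5, 0.7 and 0.9.
- Simulated, one score × two doses: about 9%.
- Simulated, only the overall three-group test on each of three scores: 14.2%, 12.8% and 8.5% at correlation 0, 0.5 and 0.9. Restoring the overall test therefore reduces the problem without removing it. The protocol also does not make the pairwise tests conditional on it.

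**If all three scores had to succeed.** With 80% power each (n = 18, d = 0.961), joint power for one dose is about 51%, 61% and 66% at correlation 0, 0.5 and 0.7. An any-score rule and an all-scores rule therefore describe very different trials, and the documents do not say which applies.

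**The case against.** The strongest reply has three parts.

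First, the protocol is not silent. Section 13.2.2.5 fixes Visit 12, percent change and a baseline-adjusted overall comparison, and 10.1 already makes physician BBSS, VAS and medication use secondary. This stands. A reader might infer that any SAP outcome could be presented as the main result, or that the visit is wholly open. The documents do not support that: a physician score or pill count put forward as primary would visibly contradict 10.1. For the same reason, a familywise count over every efficacy outcome in the SAP would mislead. It would mix near-duplicates (change and percent change of the same pill counts) with outcomes the protocol calls secondary.

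Second, this is a phase 2 trial of up to 60 women. Protocol 13.3 says the p-values quantify differences, and SAP 6.2 is open about making no adjustment. This also stands and lowers the severity. It does not dispose of the point, because both documents still declare significance at 0.05 and 13.1 states 80% power.

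Third, part of the SAP is not visible: 6.7.1, 6.7.2 and portions of section 3. A visit or window definition there cannot be excluded, and the powered variable may be named in the missing sample-size text. Nor can one infer that amenorrhea was newly added to the endpoints, since redaction marks follow some of the protocol's endpoint lists. Sections 5 and 6.7.5 do read as complete, and neither labels a primary.

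**Conclusion.** The point holds as a should-fix. The visible SAP designates no primary endpoint, visit or dose contrast, and for the patient BBSS scores it conflicts with the protocol on metric and model. Separately, the protocol's three-score primary has no success rule or dose order, and 8.1 lists it twice.

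With one visit and one metric taken as fixed, the stated rules give about a 25% (uncorrelated) to 19% (correlation 0.7) chance of at least one nominally significant patient score against placebo when neither dose works. These figures rest on 20 per arm, normal data and an assumed correlation. Leaving the metric or the choice of test open would raise them. What is at stake is how a phase 2 result is read, since the protocol does not present the p-values as confirmatory.

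**What to change.** Before unblinding:

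1. In SAP 5 and 6.7.5, label the patient BBSS as primary and the other outcomes as secondary, as protocol 10.1 does.
2. State one metric, and one window: the 28 days up to the last Stage 2 dose (Visit 12). Protocol 13.2.2.5 says only a similar period, while 13.2.2.1 and 13.2.2.8 give 28 days.
3. Use the protocol's baseline-adjusted ANCOVA, with the dose-versus-placebo contrasts taken from that model.
4. Remove the duplicate listing in protocol 8.1.
5. Write one success rule covering both scores and doses, in one of two forms:
   - One primary score, for example the total that SAP 6.7.5 already computes, with the two dose contrasts tested in a fixed order. The total is not the protocol's stated primary, so 8.1 and 10.1 would have to be aligned.
   - The three components, with a multiplicity procedure over all six score-by-dose tests. Hochberg across the three scores within each dose is not enough: by simulation it still leaves about 8% to 9% familywise error at correlations up to 0.7.

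**Cost.** SAP wording and a short protocol alignment; no new data. Under a fixed order that tests 12 mg first, 12 mg loses no power and a 6 mg claim depends on 12 mg. Simulated at d = 0.961 for 12 mg, the loss for 6 mg is about 1 point if its effect is half as large and 9 to 10 points if the effects are equal. The six-test route costs more: with Bonferroni at 0.05/6 = 0.0083, power per test at 20 per arm falls from 84.2% to 60.3%, and 28 per arm would be needed for 80%.
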